11.0 DATA SUBMISSION SCHEDULE

Case report forms with appropriate source documentation will be completed according to the schedule listed in this section.

Case Report Form	Submission Schedule
Original Consent Form	Prior to registration
On-Study Form Tumor Biopsy Form	Prior to starting treatment
Treatment Form Pill Diary	Every cycle
Toxicity Form	Continuous
Treatment Summary Form Tumor Biopsy Form	Completion of treatment
Follow Up Form	Every 2 months until death
Tumor Measurement Form	Baseline, end of every even numbered cycle, and end of treatment
MedWatch Form	See Section 7.0 for reporting requirements

12.0 MEASUREMENT OF EFFECT

12.1 Antitumor Effect – Solid Tumors

For the purposes of this study, patients should be re-evaluated for response 8 weeks after initiation of pazopanib and then every 8 weeks thereafter. In addition to a baseline scan, confirmatory scans should also be obtained not less than 4 weeks following initial documentation of objective response.

Response and progression will be evaluated in this study using the new international criteria proposed by the revised Response Evaluation Criteria in Solid Tumors (RECIST) guideline (version 1.1) [Eur J Ca 45:228-247, 2009]. Changes in the largest diameter (unidimensional measurement) of the tumor lesions and the shortest diameter in the case of malignant lymph nodes are used in the RECIST criteria.

12.2 Disease Parameters

Measurable disease: Measurable lesions are defined as those that can be accurately measured in at least one dimension (longest diameter to be recorded) as >20 mm by chest x-ray, as >10 mm with CT scan, or >10 mm with calipers by clinical exam. All tumor measurements must be recorded in millimeters (or decimal fractions of centimeters).

Malignant lymph nodes: To be considered pathologically enlarged and measurable, a lymph node must be >15 mm in short axis when assessed by CT scan (CT scan slice

thickness recommended to be no greater than 5 mm). At baseline and in follow-up, only the short axis will be measured and followed.

Non-measurable disease: All other lesions (or sites of disease), including small lesions (longest diameter <10 mm or pathological lymph nodes with ≥ 10 to <15 mm short axis), are considered non-measurable disease. Bone lesions, leptomeningeal disease, ascites, pleural/pericardial effusions, lymphangitis cutis/pulmonitis, inflammatory breast disease, and abdominal masses (not followed by CT or MRI), are considered as non-measurable.

Note: Cystic lesions that meet the criteria for radiographically defined simple cysts should not be considered as malignant lesions (neither measurable nor non-measurable) since they are, by definition, simple cysts.

‘Cystic lesions’ thought to represent cystic metastases can be considered as measurable lesions, if they meet the definition of measurability described above. However, if non-cystic lesions are present in the same patient, these are preferred for selection as target lesions.

Target lesions: All measurable lesions up to a maximum of 2 lesions per organ and 5 lesions in total, representative of all involved organs, should be identified as target lesions and recorded and measured at baseline. Target lesions should be selected on the basis of their size (lesions with the longest diameter), be representative of all involved organs, but in addition should be those that lend themselves to reproducible repeated measurements. It may be the case that, on occasion, the largest lesion does not lend itself to reproducible measurement in which circumstance the next largest lesion which can be measured reproducibly should be selected. A sum of the diameters (longest for non-nodal lesions, short axis for nodal lesions) for all target lesions will be calculated and reported as the baseline sum diameters. If lymph nodes are to be included in the sum, then only the short axis is added into the sum. The baseline sum diameters will be used as reference to further characterize any objective tumor regression in the measurable dimension of the disease.

Non-target lesions: All other lesions (or sites of disease) including any measurable lesions over and above the 5 target lesions should be identified as non-target lesions and should also be recorded at baseline. Measurements of these lesions are not required, but the presence, absence, or in rare cases unequivocal progression of each should be noted throughout follow-up.

12.3 Methods for Evaluation of Measurable Disease

All measurements should be taken and recorded in metric notation using a ruler or calipers. All baseline evaluations should be performed as closely as possible to the beginning of treatment and never more than 4 weeks before the beginning of the treatment.

The same method of assessment and the same technique should be used to characterize

each identified and reported lesion at baseline and during follow-up. Imaging-based evaluation is preferred to evaluation by clinical examination unless the lesion(s) being followed cannot be imaged but are assessable by clinical exam.

Clinical lesions: Clinical lesions will only be considered measurable when they are superficial (e.g., skin nodules and palpable lymph nodes) and ≥ 10 mm diameter as assessed using calipers (e.g., skin nodules). In the case of skin lesions, documentation by color photography, including a ruler to estimate the size of the lesion, is recommended.

Chest x-ray: Lesions on chest x-ray are acceptable as measurable lesions when they are clearly defined and surrounded by aerated lung. However, CT is preferable.

Conventional CT and MRI: This guideline has defined measurability of lesions on CT scan based on the assumption that CT slice thickness is 5 mm or less. If CT scans have slice thickness greater than 5 mm, the minimum size for a measurable lesion should be twice the slice thickness. MRI is also acceptable in certain situations (e.g. for body scans).

Use of MRI remains a complex issue. MRI has excellent contrast, spatial, and temporal resolution; however, there are many image acquisition variables involved in MRI, which greatly impact image quality, lesion conspicuity, and measurement. Furthermore, the availability of MRI is variable globally. As with CT, if an MRI is performed, the technical specifications of the scanning sequences used should be optimized for the evaluation of the type and site of disease. Furthermore, as with CT, the modality used at follow-up should be the same as was used at baseline and the lesions should be measured/assessed on the same pulse sequence. It is beyond the scope of the RECIST guidelines to prescribe specific MRI pulse sequence parameters for all scanners, body parts, and diseases. Ideally, the same type of scanner should be used and the image acquisition protocol should be followed as closely as possible to prior scans. Body scans should be performed with breath-hold scanning techniques, if possible.

PET-CT: At present, the low dose or attenuation correction CT portion of a combined PET-CT is not always of optimal diagnostic CT quality for use with RECIST measurements. However, if the site can document that the CT performed as part of a PET-CT is of identical diagnostic quality to a diagnostic CT (with IV and oral contrast), then the CT portion of the PET-CT can be used for RECIST measurements and can be used interchangeably with conventional CT in accurately measuring cancer lesions over time. Note, however, that the PET portion of the CT introduces additional data which may bias an investigator if it is not routinely or serially performed.

Ultrasound: Ultrasound is not useful in assessment of lesion size and should not be used as a method of measurement. Ultrasound examinations cannot be reproduced in their entirety for independent review at a later date and, because they are operator dependent, it cannot be guaranteed that the same technique and measurements will be taken from one assessment to the next. If new lesions are identified by ultrasound in the course of the study, confirmation by CT or MRI is advised. If there is concern about radiation

exposure at CT, MRI may be used instead of CT in selected instances.

Endoscopy, Laparoscopy: The utilization of these techniques for objective tumor evaluation is not advised. However, such techniques may be useful to confirm complete pathological response when biopsies are obtained or to determine relapse in trials where recurrence following complete response (CR) or surgical resection is an endpoint.

Tumor markers: Tumor markers alone cannot be used to assess response. If markers are initially above the upper normal limit, they must normalize for a patient to be considered in complete clinical response. Specific guidelines for both CA-125 response (in recurrent ovarian cancer) and PSA response (in recurrent prostate cancer) have been published [JNCI 96:487-488, 2004; J Clin Oncol 17, 3461-3467, 1999; J Clin Oncol 26:1148-1159, 2008]. In addition, the Gynecologic Cancer Intergroup has developed CA-125 progression criteria which are to be integrated with objective tumor assessment for use in first-line trials in ovarian cancer [JNCI 92:1534-1535, 2000].

Cytology, Histology: These techniques can be used to differentiate between partial responses (PR) and complete responses (CR) in rare cases (e.g., residual lesions in tumor types, such as germ cell tumors, where known residual benign tumors can remain).

The cytological confirmation of the neoplastic origin of any effusion that appears or worsens during treatment when the measurable tumor has met criteria for response or stable disease is mandatory to differentiate between response or stable disease (an effusion may be a side effect of the treatment) and progressive disease.

FDG-PET: While FDG-PET response assessments need additional study, it is sometimes reasonable to incorporate the use of FDG-PET scanning to complement CT scanning in assessment of progression (particularly possible 'new' disease). New lesions on the basis of FDG-PET imaging can be identified according to the following algorithm:

- Negative FDG-PET at baseline, with a positive FDG-PET at follow-up is a sign of PD based on a new lesion.
- No FDG-PET at baseline and a positive FDG-PET at follow-up: If the positive FDG-PET at follow-up corresponds to a new site of disease confirmed by CT, this is PD. If the positive FDG-PET at follow-up is not confirmed as a new site of disease on CT, additional follow-up CT scans are needed to determine if there is truly progression occurring at that site (if so, the date of PD will be the date of the initial abnormal FDG-PET scan). If the positive FDG-PET at follow-up corresponds to a pre-existing site of disease on CT that is not progressing on the basis of the anatomic images, this is not PD.
- FDG-PET may be used to upgrade a response to a CR in a manner similar to a biopsy in cases where a residual radiographic abnormality is thought to represent fibrosis or scarring. The use of FDG-PET in this circumstance should be prospectively described in the protocol and supported by disease-specific medical literature for the indication. However, it must be acknowledged that both approaches may lead to false positive CR due to limitations of FDG-PET and

biopsy resolution/sensitivity.

Note: A 'positive' FDG-PET scan lesion means one which is FDG avid with an uptake greater than twice that of the surrounding tissue on the attenuation corrected image.

12.4 Response Criteria

12.4.1 Evaluation of Target Lesions

Complete Response (CR): Disappearance of all target lesions. Any pathological lymph nodes (whether target or non-target) must have reduction in short axis to <10 mm.

Partial Response (PR): At least a 30% decrease in the sum of the diameters of target lesions, taking as reference the baseline sum diameters.

Progressive Disease (PD): At least a 20% increase in the sum of the diameters of target lesions, taking as reference the smallest sum on study (this includes the baseline sum if that is the smallest on study). In addition to the relative increase of 20%, the sum must also demonstrate an absolute increase of at least 5 mm. (Note: the appearance of one or more new lesions is also considered progressions).

Stable Disease (SD): Neither sufficient shrinkage to qualify for PR nor sufficient increase to qualify for PD, taking as reference the smallest sum diameters while on study.

12.4.2 Evaluation of Non-Target Lesions

Complete Response (CR): Disappearance of all non-target lesions and normalization of tumor marker level. All lymph nodes must be non-pathological in size (<10 mm short axis).

Note: If tumor markers are initially above the upper normal limit, they must normalize for a patient to be considered in complete clinical response.

Non-CR/Non-PD: Persistence of one or more non-target lesion(s) and/or maintenance of tumor marker level above the normal limits.

Progressive Disease (PD): Appearance of one or more new lesions and/or unequivocal progression of existing non-target lesions. Unequivocal progression should not normally trump target lesion status. It must be representative of overall disease status change, not a single lesion increase.

Although a clear progression of “non-target” lesions only is exceptional, the opinion of the treating physician should prevail in such circumstances, and the

progression status should be confirmed at a later time by the review panel (or Principal Investigator).

12.4.3 Evaluation of Best Overall Response

The best overall response is the best response recorded from the start of the treatment until disease progression/recurrence (taking as reference for progressive disease the smallest measurements recorded since the treatment started). The patient's best response assignment will depend on the achievement of both measurement and confirmation criteria.

For Patients with Measurable Disease (i.e., Target Disease)

Target Lesions	Non-Target Lesions	New Lesions	Overall Response	Best Overall Response when Confirmation is Required*
CR	CR	No	CR	>4 wks. Confirmation**
CR	Non-CR/Non-PD	No	PR	>4 wks. Confirmation**
CR	Not evaluated	No	PR	
PR	Non-CR/Non-PD/not evaluated	No	PR	
SD	Non-CR/Non-PD/not evaluated	No	SD	Documented at least once >4 wks. from baseline**
PD	Any	Yes or No	PD	no prior SD, PR or CR
Any	PD***	Yes or No	PD	
Any	Any	Yes	PD	

* See RECIST 1.1 manuscript for further details on what is evidence of a new lesion.
 ** Only for non-randomized trials with response as primary endpoint.
 *** In exceptional circumstances, unequivocal progression in non-target lesions may be accepted as disease progression.
 Note: Patients with a global deterioration of health status requiring discontinuation of treatment without objective evidence of disease progression at that time should be reported as “symptomatic deterioration.” Every effort should be made to document the objective progression even after discontinuation of treatment.

For Patients with Non-Measurable Disease (i.e., Non-Target Disease)

Non-Target Lesions	New Lesions	Overall Response
CR	No	CR
Non-CR/non-PD	No	Non-CR/non-PD*
Not all evaluated	No	not evaluated
Unequivocal PD	Yes or No	PD
Any	Yes	PD

* ‘Non-CR/non-PD’ is preferred over ‘stable disease’ for non-target disease since SD is increasingly used as an endpoint for assessment of efficacy in some trials so to assign this category when no lesions can be measured is not advised

12.4.4 Duration of Response

Duration of overall response: The duration of overall response is measured from the time measurement criteria are met for CR or PR (whichever is first recorded) until the first date that recurrent or progressive disease is objectively documented (taking as reference for progressive disease the smallest measurements recorded since the treatment started).

The duration of overall CR is measured from the time measurement criteria are first met for CR until the first date that progressive disease is objectively documented.

Duration of stable disease: Stable disease is measured from the start of the treatment until the criteria for progression are met, taking as reference the smallest measurements recorded since the treatment started, including the baseline measurements.

12.4.5 Progression-Free Survival

Progression-free survival is defined as the duration of time from start of treatment to time of progression or death, whichever occurs first.

12.4.6 Response Review

It is strongly recommended that all responses be reviewed by an expert(s) independent of the study at the study's completion.

13.0 DATA AND SAFETY MONITORING

In compliance with the Washington University Institutional Data and Safety Monitoring Plan, the Principal Investigator will provide a Data and Safety Monitoring (DSM) report to the Washington University Quality Assurance and Safety Monitoring Committee (QASMC) semi-annually beginning six months after accrual has opened (if at least five patients have been enrolled) or one year after accrual has opened (if fewer than five patients have been enrolled at the six-month mark).

The Principal Investigator will review all patient data at least every six months, and provide a semi-annual report to the QASMC. This report will include:

- HRPO protocol number, protocol title, Principal Investigator name, data coordinator name, regulatory coordinator name, and statistician
- Date of initial HRPO approval, date of most recent consent HRPO approval/revision, date of HRPO expiration, date of most recent QA audit, study status, and phase of study
- History of study including summary of substantive amendments; summary of accrual

- suspensions including start/stop dates and reason; and summary of protocol exceptions, error, or breach of confidentiality including start/stop dates and reason
- Study-wide target accrual and study-wide actual accrual
 - Protocol activation date
 - Average rate of accrual observed in year 1, year 2, and subsequent years
 - Expected accrual end date
 - Objectives of protocol with supporting data and list the number of participants who have met each objective
 - Measures of efficacy
 - Early stopping rules with supporting data and list the number of participants who have met the early stopping rules
 - Summary of toxicities
 - Abstract submissions/publications
 - Summary of any recent literature that may affect the safety or ethics of the study

The study principal investigator and Research Patient Coordinator will monitor for serious toxicities on an ongoing basis. Once the principal investigator or Research Patient Coordinator becomes aware of an adverse event, the AE will be reported to the HRPO and QASMC according to institutional guidelines.

14.0 STATISTICAL CONSIDERATIONS

14.1 Study Objectives and Endpoints

The primary objective of this study is to investigate the response rate and progression-free survival of single agent pazopanib in a molecularly selected population of patients with advanced NSCLC. Patients with advanced NSCLC and abnormalities in VEGFR or PDGFR will receive single agent pazopanib at 800 mg daily. Patients may elect at study entry to provide tissue, from either archival or freshly obtained tissue, for research purposes. Optional tumor tissue testing will include whole exome and transcriptome sequencing performed in 10 patients. This will include 4 to 6 responders and 4 to 6 non-responders in order to identify the predictors for benefit; initial predictors are the mutations in VEGFR or PDGFR, but sequencing will be used to evaluate for other predictors as well. Patients may also elect to submit tissue from any standard of care biopsy performed at the time of progression in an attempt to identify the mechanisms for secondary resistance.

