14.2 Study Design and Analyses

This is an open label, single-arm pilot study to obtain preliminary information of the efficacy of single agent pazopanib. A total of N=20 patients will be enrolled for this study. The sample size is determined primarily based on clinical feasibility rather than statistical power. According to the general guidelines regarding sample size for pilot and translational study¹⁸, however, the proposed sample size will provide us a reasonable precision to estimate the preliminary information. If 4 responders are observed out of 20

patients, for example, we would have 80% confidence that the “true” rate would fall between 9% and 36%. If the “true” response rate is 20% or higher, there would be 80% chance of observing at least 3 responders out of 20 patients. Conversely, there would be <10% chance to observe 3 or more responders if the true rate is less than 5%.

As a pilot study for proof of principal, the data analysis will be descriptive in nature. Demographic and clinical characteristics of the sample, as well as response, toxicity by grade and loss to follow up will be summarized using descriptive statistics. Kaplan-Meier product limit estimator will be used to describe the distribution of progression free survival. The 95% confidence interval (CI) for RR and 6-month PFS will also be calculated. The association between response and specific mutation status will be assessed by permutation analysis. Taking the relationship between VEGFR1 expression and RR as an example, for instance, we first compute the observed test statistics, e.g., the sample mean difference between responders versus non-responders. Then to simulate the null distribution of the test statistics, or the distribution of the observed mean differences if there were truly no difference, we repeat the following 10,000 times: we randomly shuffle the response status, and then calculate the sample difference between the newly designated groups. The permutation p-value equals the proportion of simulations from the null distribution that exceed the observed test statistics.

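### Does the aim of sequencing 4 to 6 responders conflict with a 20-patient study whose quoted chances are for 3 or more responders?

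*Combined protocol and SAP*

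**What the plan says.** Section 14.1 describes the correlative work: "Optional tumor tissue testing will include whole exome and transcriptome sequencing performed in 10 patients". It then gives the make-up of that group: "This will include 4 to 6 responders and 4 to 6 non-responders in order to identify the predictors for benefit". Participation is voluntary: "Patients may elect at study entry to provide tissue". Section 1.6 adds that archived samples need enough viable cells to be sequenced. Neither section gives an expected consent rate or usable-tissue rate.

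Section 14.2 fixes the size of the study: "A total of N=20 patients will be enrolled for this study". It says this number rests mainly on feasibility, not on power. It then offers three illustrations:

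- With 4 responders of 20, an interval from 9% to 36%, labelled as 80% confidence.
- For a favourable drug effect: "response rate is 20% or higher, there would be 80% chance of observing at least 3 responders out of 20 patients".
- For a poor one, a true rate under 5%, the probability of reaching the same count of 3 is put at under 10%.

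The same section calls the analysis descriptive and states: "The 95% confidence interval (CI) for RR and 6-month PFS will also be calculated". It names no method for that interval and sets no threshold that the interval or the responder count must meet.

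**The concern.** Read together, the two sections seem to work from different responder counts. Section 14.1 needs at least 4 responders, while the only chances quoted in Section 14.2 are for 3 or more. A reader could carry the 80% across to the sequencing aim, where it does not apply. Tissue is also optional, so some responders may not be available, and the plan does not say what happens if fewer than 4 can be sequenced. The comparison of responders with non-responders is one of the plan's routes to predictors of benefit, and Section 1.5 makes better predictors a main purpose of the study. If the group were filled after outcomes were known and without a rule, the choice of patients could look arbitrary.

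The second strand is precision. The plan supports its claim of reasonable precision with an 80% interval but will report 95% intervals, which are wider. With 3 responders, the count used in Section 14.2, the exact 95% interval still contains the 5% rate that the plan uses as its low reference.

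**Working it through.** **Inputs.** N = 20, response rates of 20% and 5%, the threshold of 3 responders and the 80% interval for 4/20 come from Section 14.2. The minimum of 4 sequenced responders comes from Section 14.1. Other response rates and all usable-tissue shares below are assumptions, shown as ranges.

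**The plan's own figures.** With X ~ Bin(20, p):

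- p = 0.20: P(0), P(1), P(2) = 0.0115, 0.0576, 0.1369. So P(X ≥ 3) = 1 − 0.2061 = 0.794 (stated: 80%).
- p = 0.05: P(X ≥ 3) = 0.0755 (stated: below 10%).
- Exact (Clopper-Pearson) 80% interval for 4/20: the lower limit is the 0.10 quantile of Beta(4, 17) and the upper limit is the 0.90 quantile of Beta(5, 16). This gives 9.0% to 36.1% (stated: 9% to 36%). Wilson gives 11.0% to 33.5% and Wald 8.5% to 31.5%, so the plan evidently used the exact method.

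All three stated figures reproduce.

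**Chance of 4 or more responders.** At p = 0.20, P(3) = 0.2054, so P(X ≥ 4) = 0.7939 − 0.2054 = 0.589. The expected count is 20 × 0.20 = 4.

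| True rate | P(X ≥ 4 of 20) |
|---|---|
| 10% | 13% |
| 15% | 35% |
| 20% | 59% |
| 25% | 77% |

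If a share t of responders has consent and usable tissue, the sequenced count is Bin(20, 0.20t):

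| Assumed t | P(4 or more sequenced responders) |
|---|---|
| 90% | 50% |
| 80% | 40% |
| 70% | 30% |
| 50% | 13% |

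**Intervals at the reported level.** Exact 95%: 4/20 gives 5.7% to 43.7%, a width of 38 points against 27 for the 80% interval (36.1 − 9.0). 3/20 gives 3.2% to 37.9%. Whether 3/20 excludes 5% depends on the method: the lower limit is 3.2% exact and 4.0% mid-P, but 5.2% by Wilson.

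**What fewer than 4 responders would affect.** The response rate with its interval and the Kaplan-Meier estimate do not depend on who is sequenced. The permutation analysis of response against mutation status can use the target-gene results that inclusion criterion 1 in Section 3.1 requires of every patient. Only the exploratory sequencing contrast gets smaller. As an illustration, keep ten places: 4 against 6 allows 10!/(4!·6!) = 210 groupings and 3 against 7 allows 10!/(3!·7!) = 120. Either is a hypothesis-generating comparison, and the difference is one of degree.

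**The case for a change.** The best argument for a change needs no outside benchmark, because 4 is the plan's own number. At a true rate of 20% there is a 41% chance (1 − 0.589) that the group described in Section 14.1 cannot be formed even if every responder gives good tissue. The documents also give reasons to expect worse. Section 1.5 anticipates that only a small proportion will benefit, Section 1.2 calls earlier single-agent response rates disappointing, and Section 3.1 admits patients with evaluable but non-measurable disease, for whom the response table in Section 12.4.3 has no partial response. A rule for filling the places would cost little and would best be set before outcomes are seen.

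The arithmetic of this stands, and so does the remark that Section 14.1 words an outcome-dependent count as if it were certain. The need for a remedy does not. The obvious handling is to sequence every responder with usable tissue and add non-responders, which any analyst would do unprompted. A more elaborate rule, such as filling places with patients at the extremes of progression-free survival, would replace the responder contrast with a comparison on another endpoint. Statisticians could reasonably disagree on whether that is better.

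On precision, a 95% interval is always wider than an 80% one. The plan labels its example as 80%, computes it correctly and separately commits to 95% intervals for the report. Excluding 5% is not a criterion anywhere in the plan.

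**Conclusion.** The concern does not call for a change. Sections 14.1 and 14.2 do not contradict each other: the 80% belongs to 3 or more responders and is right for that event, nothing is claimed for 4 or more, and the sample size was not derived from either count. The target of 4 to 6 is in line with the 4 responders expected at a 20% rate.

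What is left is an optional, exploratory target stated too firmly. Its chance of being met is 59% at a true rate of exactly 20%, and 77% at 25% (the plan speaks of 20% or higher). It is lower if the response rate is lower or tissue is lost; the tissue figures rest wholly on assumed shares. Missing the target would leave a smaller sequencing comparison and would alter no estimate, interval or decision in the main analysis. Quoting 6% to 44% beside 9% to 36% would make Section 14.2 a little more candid, but the reported results would be the same.
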